**The following medications or treatments are prohibited 6 months prior to Visit 1 and throughout the study:**

- Therapeutic or cosmetic botulinum toxin injections (eg, Dysport®, BOTOX®, Xeomin®, Myobloc®, Jeuveau™) into areas of the head, face, or neck.
- Injectable monoclonal antibodies blocking the CGRP pathway (eg, Aimovig™, Emgality™, Ajovy®)

## 12.2 Classification of Migraine Preventive Medications

Below is a list of migraine preventive medications considered effective or probably effective sorted by mechanism of action. Of note, topiramate and valproic acid derivatives are considered separate categories.

Pharmacologic Category	Drug Name
Antiepileptic	Valproic acid, sodium valproate, divalproex sodium Topiramate
Tricyclic antidepressant	Amitriptyline Nortriptyline
Beta-blockers	Metoprolol Bisoprolol Atenolol Nadolol Propranolol Timolol
Calcium channel blocker	Flunarizine
Angiotensin receptor blocker (ARB)	Candesartan
Angiotensin-converting enzyme (ACE) inhibitor	Lisinopril
Serotonin-norepinephrine reuptake inhibitor (SNRI)	Desvenlafaxine Venlafaxine
Miscellaneous	Country approved products for migraine prevention (eg, oxetrone, pizotifen)

Source: [Evers 2009](#), [Hoffmann 2014](#), [Schürks 2008](#), [Silberstein 2012](#), [Steiner 2007](#).

## 12.3 Glossary of Abbreviations

Term/Abbreviation	Definition
AE	adverse event
AESI	adverse event of special interest
ALT	alanine aminotransferase
AST	aspartate aminotransferase
BP	blood pressure
CBD	cannabidiol
CGRP	calcitonin gene-related peptide
CM	chronic migraine
C-SSRS	Columbia-Suicide Severity Rating Scale
CYP3A4	cytochrome P450 3A4
DSMB	Data Safety Monitoring Board
ECG	electrocardiogram
eCRF	electronic case report form
EM	episodic migraine
EOS	end of study
ET	early termination
FDA	Food and Drug Administration
GBD 2010	Global Burden of Disease Survey 2010
GCP	Good Clinical Practice
HIPAA	Health Insurance Portability and Accountability Act
HSG	hysterosalpingogram
IB	Investigator's Brochure
ICF	informed consent form
ICH	International Conference on Harmonisation
ICHD-3	International Classification of Headache Disorders, 3 rd edition
IEC	Independent Ethics Committee
IgM	immunoglobulin M
INR	international normalized ratio
IRB	Institutional Review Board
IUD	intrauterine device
IUS	intrauterine hormone releasing system
IV	intravenous
IWRS	interactive web response system
NSAID	nonsteroidal anti-inflammatory drug
OATP1B1	organic anion transporting polypeptide 1B1
PK	pharmacokinetic
QTcF	QT interval corrected for heart rate using Fridericia formula (QTcF = QT/(RR) 1/2 )

Term/Abbreviation	Definition
SAE	serious adverse event
SNRI	serotonin norepinephrine reuptake inhibitor
SSRI	selective serotonin reuptake inhibitor
SUSAR	suspected unexpected serious adverse reaction
ULN	upper limit of normal

**To:** Atogepant 3101-309-002 Institutional Review Boards & Investigators

**From:** [REDACTED] /Clinical Development, CNS

**Date:** 23 March 2020

**Re:** **3101- 309-002, A PHASE 3, MULTICENTER, OPEN-LABEL 40-WEEK EXTENSION STUDY TO EVALUATE THE LONG-TERM SAFETY AND TOLERABILITY OF ORAL ATOGEPEANT FOR THE PREVENTION OF MIGRAINE IN PARTICIPANTS WITH EPISODIC MIGRAINE**

---

Please accept this correspondence as notification that due to the COVID-19 pandemic the protocol changes below may be implemented for Investigative Sites to eliminate immediate potential hazards to participants and study staff while ensuring participant safety and maintaining data integrity.

- **Remote Study Visits (Visit 2 - Visit 11)** – Investigators/appropriately designated study staff will be allowed to perform study visits as remote study visits (e.g., conducted via phone, video conference) if participants are unable to attend in-person due to the COVID-19 pandemic. During these remote study visits, the *Schedule of Visits and Procedures for Remote Study Visits* below should be followed. Please note the following clarifications:
  - **Safety Assessments:**
    - Safety assessments to be completed at remote study visits include assessment of adverse events, concomitant medications, pregnancy test results review, and the Columbia-Suicide Severity Rating Scale (C-SSRS).
    - For participants that have a study visit replaced by a remote study visit, all missed in-person safety assessments (i.e., clinical laboratory samples, vital signs and ECGs) will be collected at the next in-person visit.
    - To ensure patient safety, remote study visits can be performed for up to 8 weeks (ie, no in-person study visits for up to 8 weeks) at the discretion of the Investigator after which participants who cannot attend in-person for a study visit must be discontinued from the study.
  - **Columbia-Suicide Severity Rating Scale (C-SSRS)** – Study trained, and delegated raters will perform the C-SSRS remotely and review any positive results with an Investigator-delegated clinician to ensure the participant is not at risk for suicide.
  - **Urine Pregnancy Tests** – Investigators/site staff will provide participants with study supplied urine pregnancy tests and corresponding written instructions to be used at-home by participants for remote study visits. Sites are required to verbally review testing instructions with all participants. Pregnancy tests must be completed according to the *Schedule of Visits and Procedures for Remote Visits* below.
- **Study Medication Dispensation for Remote Study Visits (Visit 2 – Visit 10):**
  - Study medication for remote study visits can be shipped to participants via an overnight courier or provided curbside.
  - Study medication to cover 1 additional remote study visit may be dispensed.
  - Sites are required to provide a documented written process with approval from Allergan prior to performing the first remote visit.

- **Study Visit 12/Follow-Up/End of Study** – Study Visit 12 should be conducted remotely (e.g., conducted via phone, video conference) for all participants in all cases following the *Schedule of Visits and Procedures for Remote Study Visits* below.

Training on this protocol clarification will be provided by Allergan. We appreciate your dedication in ensuring participant safety during this challenging time. If you have any questions, please do not hesitate to contact your RSM or the Medical Monitor.

## 3101-309-002 Schedule of Visits and Procedures for Remote Study Visits

Study Period	Open-label Treatment Period (40 weeks)										Safety Follow-up Period (4 weeks)
	Visit #	Visit 2	Visit 3	Visit 4	Visit 5	V sit 6	Visit 7	Visi 8	Visit 9	Visit 10	
Day/Week	Week 4 (Day 28)	Week 8 (Day 56)	Week 12 (Day 84)	Week 16 (Day 112)	Week 20 (Day 140)	Week 24 (Day 168)	Week 28 (Day 196)	Week 32 (Day 224)	Week 36 (Day 252)	Week 40 (Day 280)	Week 44 (Day 308)
Visit Windows	± 3 days	± 3 days	± 3 days	± 3 days	± 3 days	± 3 days	± 3 days	± 3 days	± 3 days	± 3 days	± 3 days
Provide urine pregnancy test and instructions a	X	X	X	X	X	X	X	X	X	X	X
C-SSRS	X	X	X	X	X	X	X	X	X	X	X
Access IWRS	X	X	X	X	X	X	X	X	X	X	X
Dispense study intervention	X	X	X	X	X	X	X	X	X	X	X
Review of study intervention compliance and accountability	X	X	X	X	X	X	X	X	X	X	
Adverse Events	X	X	X	X	X	X	X	X	X	X	X
Concomitant medications/concurrent procedures	X	X	X	X	X	X	X	X	X	X	X

a For women of childbearing potential only, a urine pregnancy test must be performed within 48 hours of the remote visits.

3.0 LIST OF ABBREVIATIONS

Term/Abbreviation	Definition
AE	adverse event
ALT	alanine aminotransferase
AST	aspartate aminotransferase
BP	blood pressure
CM	chronic migraine
C-SSRS	Columbia-Suicide Severity Rating Scale
ECG	electrocardiogram
eCRF	electronic case report form
EM	episodic migraine
EOS	end of study
ET	early termination
FDA	Food and Drug Administration
GCP	Good Clinical Practice
ICF	informed consent form
ICH	International Conference on Harmonisation
ICHD-3	International Classification of Headache Disorders, 3 rd edition
LLN	low limit of normal
MedDRA	Medical Dictionary for Regulatory Activities
OL	open-label
PCS	potentially clinically significant
PID	participant identification
PK	pharmacokinetic
PT	preferred term
QTc	QT interval corrected for heart rate
QTcF	QT interval corrected for heart rate using Fridericia formula ($QTcF = QT/(RR)^{1/4}$)
SAE	serious adverse event
SAP	statistical analysis plan
SAS	statistical analysis software
SD	standard deviation
SI	Le Système International d'Unités (International System of Units)
SOC	system organ class
TEAE	treatment emergent adverse event
TESAE	treatment emergent serious adverse event
ULN	upper limit of normal
V	Visit
WHO	World Health Organization
WK	Week

4.0 INTRODUCTION

This statistical analysis plan (SAP) provides a more technical and detailed elaboration of the statistical analyses of the safety data as outlined and/or specified in the final protocol of Study 3101-309-002 (dated 22 Feb 2019) and protocol amendment 1 (dated 15 Sept 2020). Specifications of tables, figures, and data listings are contained in a separate document.

Study 3101-309-002 is a Phase 3, multicenter, open-label, 40-week, long-term safety extension study conducted in the United States and will enroll approximately 750 participants from the United States. Participants will be treated with atogepant 60 mg once daily.

The study will consist of a 40-week open-label treatment period, and a safety follow-up period of 4 weeks.

Participants will directly rollover from Study 3101-301-002 (Phase 3 EM). As such, participants will have Visit 7 from Study 3101-301-002 function as the Visit 1 for this study after the participant signs the informed consent. After Visit 1, study visits will occur every 4 weeks for the duration of the study. An EOS Visit will occur 4 weeks after the last dose of atogepant.

Note, there may be participants who complete Visit 7 in the lead-in Study 3101-301-002 before extension Study 3101-309-002 has been initiated. Those participants should complete Visit 7/ET and Visit 8/EOS Visit (including discontinuation of study intervention) per the Study 3101-301-002 Schedule of Visits and Procedures.

[figure not shown]
Depending on the timing of the initiation of this extension study, in relation to each participant's planned Visit 8 schedule, Visit 1 Study 3101-309-002 can be conducted on the same day as Visit 8/EOS Visit for Study 3101-301-002 or soon thereafter.

- If this extension study is initiated prior to the participant's planned Visit 8 in the lead-in study, then Visit 8/EOS Visit for Study 3101-301-002 should be conducted on the same day as Visit 1 for Study 3101-309-002.
- If this extension study is not initiated prior to the participant's planned Visit 8 in the lead-in study (ie, there is a gap between Visit 8 and Visit 1), then Visit 8/EOS Visit should be conducted as planned per the Study 3101-301-002 Schedule of Visits and Procedures. When this extension study is initiated, the participant should return to the clinic as soon as possible, and Visit 1 should be conducted per the Study 3101-309-002 Schedule of Visits and Procedures.

After Visit 1, study visits will occur every 4 weeks for the duration of the 40-week treatment period. Participants will return to the clinic for safety assessments at 4, 8, 12, 16, 20, 24, 28, 32, 36 and 40 weeks relative to Visit 1 (Day 1). An EOS Visit will occur 4 weeks after the last dose of atogepant 60 mg once daily. For details, Please see [Table 4-1](#) Study Design Diagram, and [Figure 4-1](#) Schedule of Visits and Procedures.

To eliminate immediate potential hazards to participants and study staff due to the COVID-19 pandemic while ensuring participant safety and maintaining data integrity, the protocol has been updated to allow investigators/appropriately designated study staff to perform study visits remotely in protocol amendment 1. For the schedule of visits and procedures conducted remotely, see [Table 4-2](#).

Figure 4-1 Study Design Diagram

ET = early termination; V = visit; Wk = week.

Table 4-1 Schedule of Visits and Procedures for In-person Visits Conducted Prior to or During the COVID-19 Pandemic

Study Period		Open-label Treatment Period (40 weeks)							Safety Follow-up Period (4 weeks)			
Visit #	Visit 1 ^a	Visit 2	Visit 3	Visit 4	Visit 5	Visit 6	Visit 7	Visit 8	Visit 9	Visit 10	Visit 11/ET	Visit 12/EOS ^e
Day/Week	Day 1 (Day 28)	Week 4 (Day 56)	Week 8 (Day 84)	Week 12 (Day 112)	Week 16 (Day 140)	Week 20 (Day 168)	Week 24 (Day 196)	Week 28 (Day 224)	Week 32 (Day 252)	Week 36 (Day 280)	Week 40 (Day 280)	Week 44 (Day 308)
Obtain Informed Consent and participant privacy												
Access IWRS	X	X	X	X	X	X	X	X	X	X	X	X
Assess inclusion/exclusion criteria	X											
Perform physical examination	X											X
Collect vital sign measurements ^b	X	X	X	X	X	X	X	X	X	X	X	X
Perform ECG	X							X			X	
Perform urine pregnancy test ^c	X	X	X	X	X	X	X	X	X	X	X	X
Clinical laboratory determinations ^d	X	X	X	X	X	X	X	X	X	X	X	X
C-SSRS	X	X	X	X	X	X	X	X	X	X	X	X
Dispense study intervention (ie, atogepant)	X	X	X	X	X	X	X	X	X	X	X	
Review of study intervention (ie, atogepant) compliance and accountability		X	X	X	X	X	X	X	X	X	X	
Adverse Events	X	X	X	X	X	X	X	X	X	X	X	X
Concomitant medications/concurrent procedures	X	X	X	X	X	X	X	X	X	X	X	X

C-SSRS = Columbia Suicide Severity Rating Scale; ECG = electrocardiogram; EOS = end of study; ET = early termination; INR = international normalized ratio; IWRS = interactive web response system.

^a After providing informed consent for the current study, Visit 1 will be conducted on the same day as Study 3101-301-002 Visit 7; procedures collected as part of Study 3101-301-002 Visit 7 should not be repeated. Visit 1 must be conducted as an in-person visit.

^b Vital sign measurements: Weight, sitting and standing blood pressure, and body temperature.

^c For women of child-bearing potential only, a urine pregnancy test will be performed at all visits.

^d Clinical laboratory determinations include chemistry, hematology, coagulation parameters (INR), and urinalysis to be collected for all visits. Samples for serology and the urine drug screen will be collected only at screening (Visit 1).

^e During the COVID-19 pandemic, Visit 12 (Follow-up/End of Study) should be conducted remotely for all participants.

Table 4-2 Schedule of Visits and Procedures for Visits Conducted Remotely Due to the COVID-19 Pandemic

Study Period	Open-label Treatment Period (40 weeks) ^a								Safety Follow-up Period (4 weeks) Visit 12/ EOS ^c		
	Visit #	Visit 2	Visit 3	Visit 4	Visit 5	Visit 6	Visit 7	Visit 8	Visit 9	Visit 10	Visit 11/ET
Day/Week	Week 4 (Day 28)	Week 8 (Day 56)	Week 12 (Day 84)	Week 16 (Day 112)	Week 20 (Day 140)	Week 24 (Day 168)	Week 28 (Day 196)	Week 32 (Day 224)	Week 36 (Day 252)	Week 40 (Day 280)	Week 44 (Day 308)
Visit Windows	± 3 days	± 3 days	± 3 days	± 3 days	± 3 days	± 3 days	± 3 days	± 3 days	± 3 days	± 3 days	± 3 days
Access IWRS	X	X	X	X	X	X	X	X	X	X	X
Provide urine pregnancy test and instructions ^b	X	X	X	X	X	X	X	X	X	X	X
C-SSRS	X	X	X	X	X	X	X	X	X	X	X
Dispense study intervention (ie, atogepant)	X	X	X	X	X	X	X	X	X	X	X
Review of study intervention (ie, atogepant) compliance and accountability	X	X	X	X	X	X	X	X	X	X	X
Adverse Events	X	X	X	X	X	X	X	X	X	X	X
Concomitant medications/concurrent procedures	X	X	X	X	X	X	X	X	X	X	X

C-SSRS = Columbia Suicide Severity Rating Scale; ECG = electrocardiogram; EOS = end of study; IWRS = interactive web response system.

^a For participants who have a study visit replaced by a remote study visit, all missed in-person safety assessments (clinical laboratory determinations, vital signs, and ECGs) will be collected at the next in-person visit. To ensure participant safety, remote study visits can be performed for up to 8 weeks at the discretion of the investigator, after which, participants who cannot attend in-person for a study visit must be discontinued from the study.

^b For women of childbearing potential only, a urine pregnancy test must be performed within 48 hours prior to the remote visits. Investigators/site staff will provide participants with study-supplied urine pregnancy tests and corresponding written instructions to be used at home by participants for remote study visits. Sites are required to verbally review testing instructions with all participants.

^c During the COVID-19 pandemic, Visit 12 (Follow-up/End of Study) should be conducted remotely for all participants.

5.0 OBJECTIVES

The study objective is to evaluate the safety and tolerability of treatment with atogepant 60 mg once daily for the prevention of migraine over a 40-week duration.

6.0 ANALYSIS POPULATIONS

6.1 SCREENED POPULATION

The Screened Population consists of all participants who signed an informed consent form to enroll in this study.

6.2 SAFETY POPULATION

The Safety Population consists of all participants who received at least 1 dose of atogepant in this extension study.

7.0 PARTICIPANT DISPOSITION

Screen-failures and the associated reasons for failure will be tabulated for all screened participants.

The number of participants in the 2 study populations (Screened, Safety) will be summarized overall.

The number of participants in the safety population will be summarized by lead-in study treatments (placebo, Atogepant 10 mg, Atogepant 30 mg, Atogepant 60 mg) and enrollment category (3101-301-002 Visit 7 Completer, 3101-301-002 Visit 8 Completer, 3101-301-002 Study Completer) and overall.

The number and percentage of participants who enter the open-label treatment period, complete the open-label treatment period and of participants who prematurely discontinue during the same period will be presented for the Safety Population. The reasons for premature discontinuation from the open-label treatment period will be summarized (number and percentage). Similar disposition information to the treatment period will be presented for the safety follow-up period. All participants who prematurely discontinue during the open-label treatment period or the safety follow-up period will be listed by discontinuation reason.

8.0 DEMOGRAPHICS AND OTHER BASELINE CHARACTERISTICS

Demographic parameters (age; age group[<20, 20-29, 30-39, 40-49, 50-59, 60-69, and >=70]; race; race group [white, non-white]; ethnicity; sex), baseline characteristics (weight; height; and body mass index, calculated as weight [kg]/(height [m])² will be summarized descriptively for the Safety Population. For all participants in 3101-309-002, demographics and other baseline characteristics from the lead-in study (Study 3101-301-002) will be used. Continuous variables will be summarized by number of participants and mean, standard deviation (SD), median, first quartile (Q1), third quartile (Q3), minimum, and maximum values. Categorical variables will be summarized by number and percentage of participants.

Abnormalities in participants' medical and surgical history will be coded using the Medical Dictionary for Regulatory Activities, version 22.0 or newer. The number and percentage of participants with abnormalities in medical and surgical histories from the lead-in study in each system organ class and preferred term will be summarized for the Safety Population.

Migraine history, including diagnosis, duration of disorder, use of migraine prevention medication in the past, average number of migraine or headache days per month in the last 3 months, acute medications taken to treat migraine headaches, and advice on lifestyle alterations from the lead-in study will be reported for the Safety Population.

Prior medication is defined as any medication taken before the date of the first dose of lead-in study treatment. *Concomitant medication* is defined as any medication taken on or after the date of the first dose of open-label study treatment.

The number and percentage of participants will be tabulated by Anatomical Therapeutic Chemical (ATC) 4 class and preferred term (PT) for both prior medications and concomitant medications in the Safety Population. Concomitant medications will be summarized for the open-label treatment period and safety follow-up period respectively.

If a participant took a specific medication multiple times or took multiple medications within a specific therapeutic class, that participant would be counted only once for the coded drug name or therapeutic class. Any prior and concomitant medications will be included in listings. The World Health Organization (WHO) Drug Dictionary Enhanced, March 2019 or newer, will be used to classify prior and concomitant medications by therapeutic class and drug name.

Protocol deviations will be defined in Protocol Deviation Requirement Specification, including significant deviation classification. The number and percentage of participants with significant protocol deviations will be summarized for the Safety Population.

9.0 EXTENT OF EXPOSURE AND TREATMENT COMPLIANCE

9.1 EXTENT OF EXPOSURE

Exposure to study treatment for the Safety Population during the treatment period will be summarized for treatment duration, calculated as the number of days from the date of the first dose of open-label study treatment taken to the date of the last dose taken, inclusive. The number and percentage of participants with each treatment duration of ≥ 1 day, ≥ 28 days, ≥ 56 days, ≥ 84 days, ≥ 90 days, ≥ 112 days, ≥ 140 days, ≥ 168 days, ≥ 180 days, ≥ 196 days, ≥ 224 days, ≥ 252 days, ≥ 270 days, ≥ 280 days will be summarized. Descriptive statistics (number of participants, mean, SD, median, Q1, Q3, minimum, and maximum) will also be summarized.

Participant-years, defined as exposure to the study treatment in years, will be summarized for the Safety Population.

9.2 MEASUREMENT OF TREATMENT COMPLIANCE

Dosing compliance for a specified period is defined as the total number of study medications actually taken by a participant during that period divided by the number of open-label study medications that were expected to be taken during the same period multiplied by 100. The total number of tablets actually taken during the treatment period will be calculated from the study medication record. Descriptive statistics for open-label study medication dosing compliance together with the compliance categories (<80%, 80% - 120%, >120%) will be summarized for open-label study treatment period between 2 consecutive visits, as well as for the period from the first dose of the open-label study interventions actually taken to the last dose of open-label study intervention actually taken for the Safety Population.

10.0 EFFICACY ANALYSES

No efficacy analysis is planned.

11.0 SAFETY ANALYSES

The safety analysis will be performed using the Safety Population. The safety parameters will include adverse events (AEs), clinical laboratory, vital sign, electrocardiographic (ECG), and C-SSRS. For each of the clinical laboratory, vital sign, and ECG parameters, the last non-missing safety assessment before the first dose of treatment from lead-in study (Study 3101-301-002) will be used as the baseline. Continuous variables will be summarized by number of participants and mean, SD, median, Q1, Q3, minimum, and maximum values. Categorical variables will be summarized by number and percentage of participants.

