**General Statistical Methods and Types of Analyses:**

The safety parameters will include AEs, clinical laboratory determinations, vital sign measurements, ECG parameters, and the C-SSRS. For each of the clinical laboratory determinations, vital sign measurements, and ECG parameters, the last non-missing safety assessment before the first dose of treatment will be used as the baseline for all analyses of that safety parameter. For all participants, baseline in lead-in study (Study 3101-301-002) will be used. Continuous variables will be summarized by the number of participants and mean, standard deviation (SD), median, minimum, and maximum values. Categorical variables will be summarized by number and percentage of participants.

*Sample Size Calculation:*

As this is a safety extension study, all eligible participants from lead-in Study 3101-301-002 may be enrolled.

**Figure 1.** Study Diagram

ET = early termination; V = visit; Wk = week.

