## **3 Study Design**

### **3.1 Structure**

This is a multicenter, open-label, 40-week, long-term safety extension study conducted in the United States and will enroll approximately 750 participants from approximately 110 sites. Participants will be treated with atogepant 60 mg once daily.

The study will consist of a 40-week open-label treatment period, and a safety follow-up period of 4 weeks.

Participants will directly rollover from Study 3101-301-002 (Phase 3 EM). As such, participants will have Visit 7 from Study 3101-301-002 function as the Visit 1 for this study after the participant signs the informed consent. After Visit 1, study visits will occur every 4 weeks for the duration of the study. An EOS Visit will occur 4 weeks after the last dose of atogepant.

Note, there may be participants who complete Visit 7 in the lead-in Study 3101-301-002 before extension Study 3101-309-002 has been initiated. Those participants should complete Visit 7/ET and Visit 8/EOS Visit (including discontinuation of study intervention) per the Study 3101-301-002 Schedule of Visits and Procedures.

Depending on the timing of the initiation of this extension study, in relation to each participant's planned Visit 8 schedule, Visit 1 Study 3101-309-002 can be conducted on the same day as Visit 8/EOS Visit for Study 3101-301-002 or soon thereafter.

- If this extension study is initiated prior to the participant's planned Visit 8 in the lead-in study, then Visit 8/EOS Visit for Study 3101-301-002 should be conducted on the same day as Visit 1 for Study 3101-309-002.
- If this extension study is not initiated prior to the participant's planned Visit 8 in the lead-in study (ie, there is a gap between Visit 8 and Visit 1), then Visit 8/EOS Visit should be conducted as planned per the Study 3101-301-002 Schedule of Visits and Procedures. When this extension study is initiated the participant should return to the clinic as soon as possible, and Visit 1 should be conducted per the Study 3101-309-002 Schedule of Visits and Procedures.

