## **7.2 Hypothesis and Methods of Analysis**

### **7.2.1 Safety Analyses**

The safety analyses will be performed using the safety population. The safety parameters will include AEs, clinical laboratory evaluations, vital sign measurements, ECG parameters, and the C-SSRS. For each of the clinical, laboratory, vital sign, and ECG parameters, the baseline value as defined for the lead-in study (3101-301-002) will be used as the baseline in this extension study (3101-309-002).

Continuous variables will be summarized by the number of participants, and mean, SD, median, minimum, and maximum values. Categorical variables will be summarized by number and percentage of participants.

Due to the COVID-19 pandemic, the study conduct and participants may be impacted. As per FDA guidance ([FDA 2020](#)), specific tables and listings will be generated to present the impact. In addition, analyses to further address the impact may be conducted.

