11.2 CLINICAL LABORATORY PARAMETERS

Descriptive statistics for clinical laboratory values (in SI units) at baseline, postbaseline, and changes from baseline values at each postbaseline timepoint will be presented for the following laboratory parameters.

In addition, descriptive statistics for values and changes from the baseline values in conventional units at each assessment time point will be presented for selected clinical laboratory parameters listed in [Appendix I](#). A description of reporting the lab values in conventional units in patient narratives (along with the standard reporting in SI units) is presented at the end of [Appendix I](#).

Hematology: Hemoglobin, hematocrit, red blood cell count, red blood cell indices (mean corpuscular volume, mean corpuscular hemoglobin, mean corpuscular hemoglobin concentration), white blood cell count, including differential (neutrophils, lymphocytes, monocytes, eosinophils, and basophils), platelet count

Chemistry: Sodium, potassium, chloride, bicarbonate, glucose, blood urea nitrogen, creatinine, total bilirubin, alkaline phosphatase, aspartate aminotransferase, alanine aminotransferase, lactate dehydrogenase, creatine kinase, total protein, albumin, calcium, phosphorus, uric acid, total cholesterol, estimated glomerular filtration rate

Urinalysis: Specific gravity, pH

Clinical laboratory test values will be considered potentially clinically significant (PCS) if they meet either the lower-limit or higher-limit PCS criteria listed in [Table 11-1](#). The number and percentage of participants who have PCS postbaseline clinical laboratory values will be tabulated. The percentages will be calculated relative to the number of participants with available non-PCS baseline values and at least 1 postbaseline assessment. The numerator will be the total number of participants with available non-PCS baseline values and at least 1 PCS postbaseline value during the study. A supportive tabular display of participants with PCS postbaseline values will be provided, including the participant identification (PID) number, baseline and all postbaseline (including non-PCS) values.

In addition, a tabular display showing all AEs that occurred in participants who had PCS postbaseline clinical laboratory values will be provided.

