18.3 REPEATED OR UNSCHEDULED ASSESSMENTS OF SAFETY PARAMETERS

Baseline is defined as the last assessment made before the first dose of lead-in study treatment. If end-of-study assessments are repeated or if unscheduled visits occur, the last nonmissing postbaseline assessment will be used as the end-of-study assessment for generating summary statistics. However, all postbaseline assessments will be used for PCS value determinations, and all assessments will be presented in the data listings.

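### For lead-in placebo participants, the lead-in baseline mixes change on placebo with change over the 40 weeks on atogepant; tables from the last value before the first open-label dose should be added for that group

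*SAP*

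**What the plan says.** The baseline rule is stated four times and agrees each time.

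- SAP 11.0: "the last non-missing safety assessment before the first dose of treatment from lead-in study (Study 3101-301-002) will be used as the baseline".
- SAP 18.3: "Baseline is defined as the last assessment made before the first dose of lead-in study treatment".
- Protocol 7.2.1: "the baseline value as defined for the lead-in study (3101-301-002) will be used as the baseline in this extension study (3101-309-002".
- Protocol Summary, statistical methods: "For all participants, baseline in lead-in study (Study 3101-301-002) will be used".

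No exception is made by lead-in arm or by route of entry. SAP 7.0 lists four lead-in treatments (placebo and atogepant 10, 30 and 60 mg) and three enrollment categories, "3101-301-002 Visit 7 Completer, 3101-301-002 Visit 8 Completer, 3101-301-002 Study Completer", but splits only participant counts by them. SAP 14.0 plans no subgroup analysis.

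The baseline value enters the results in two ways: through change from baseline at each visit, and through PCS counts. For laboratory values SAP 11.2 says: "The percentages will be calculated relative to the number of participants with available non-PCS baseline values and at least 1 postbaseline assessment". SAP 11.4 uses the same condition for ECG, and SAP 11.3 for the orthostatic measures.

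**The concern.** The objective is safety and tolerability over 40 weeks of atogepant 60 mg. The study has no control arm, so change from a value taken before atogepant is its main internal reference for laboratory, vital sign and ECG results.

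For a lead-in placebo participant, the planned reference lies a whole placebo period before the first atogepant dose. Whatever moved during that period is carried into every later change. A value that became PCS on placebo and stays so is counted among the postbaseline PCS results. The rule is not simply conservative either. A participant who was PCS at lead-in baseline and normal at entry drops out of the laboratory, ECG and orthostatic denominators, and drift in the opposite direction can hide a real change on drug.

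Adverse events are handled differently: SAP 11.1 summarizes only those starting on or after the first open-label dose. The measured parameters have no matching restriction to change that arose in this study.

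**Working it through.** There is no planned figure to reproduce. The 750 in SAP 16.0 rests on an expected completion rate that is not given, and no sample size calculation was made. The check is therefore a trace through the rules, followed by illustrations on assumed inputs.

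**Is a later pre-dose value available?** Protocol 8.4.1.1 lists vital signs with weight, ECG and laboratory samples at Visit 1, with dispensing as the last item. Under Table 1 footnote a, procedures done at lead-in Visit 7 are not repeated, so for direct rollovers the Visit 7 values serve. The current protocol does not say outright that the assessments precede the first dose, but the order of the list implies it.

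**Who is affected?** For lead-in placebo participants, all time before the first open-label dose is atogepant-free. For the three atogepant arms it is not, and only the lead-in baseline precedes all exposure.

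**Which results depend on the baseline value?**

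- Weight (SAP Table 11-3): a 7% change in either direction, with no observed-value criterion. Fully exposed.
- QTc: the increase above 60 msec in Table 11-4, and the QTcF increases above 30 and above 60 msec in SAP 11.4. Exposed; the Visit 1 QTcF limit caps the level, not the change.
- Laboratory PCS: exposed where protocol 8.9 sets no numeric Visit 1 limit, for example creatine kinase, eGFR and hematology. Carry-over is restricted for ALT/AST, bilirubin and albumin.
- Blood pressure and pulse PCS: observed value and change are both required, so drift alone is not enough. Their denominator needs only an available baseline.
- Single-value hepatic categories (Table 11-2) and QTcF above 450, 480 or 500 msec: baseline value not used.

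**Illustration 1: weight change of at least 7% in either direction at one end visit.** Assumptions, none from the documents: no drug effect, random walk, 40-week SD s of 3%, 4% or 5%, a 12-week lead-in (so 52 weeks from lead-in baseline), placebo share 25%.

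P = 2 × [1 − Φ(7 / (s × √(w/40)))], with w = 40 from a Visit 1 baseline and w = 52 from the lead-in baseline.

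- s = 3: 1.96% becomes 4.07%; difference 2.11 points; × 0.25 = 0.53 points pooled, about 4 of 750.
- s = 4: 8.01% becomes 12.48%; difference 4.47 points; × 0.25 = 1.12 points pooled, about 8 of 750.
- s = 5: 16.15% becomes 21.95%; difference 5.80 points; × 0.25 = 1.45 points pooled, about 11 of 750.

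**Illustration 2: weight gain only, with separate placebo-period drift.** Assumptions: open-label SD 4%, drift mean m and SD d independent of it, and 0.25 × 750 = 187.5 placebo participants. P = 1 − Φ((7 − m) / √(4² + d²)). From a Visit 1 baseline it is 4.0%.

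- m = 0, d = 2: 5.9%, 3.5 extra participants, 0.5 points of 750.
- m = 0.5, d = 2: 7.3%, 6.2 extra, 0.8 points.
- m = 1, d = 3: 11.5%, 14.1 extra, 1.9 points.

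**Illustration 3: PCS status already present at entry.** If a share q of placebo participants is non-PCS at lead-in baseline but PCS by Visit 1, the number is 750 × placebo share × q. For shares of 20% to 30%, q = 1% gives 1.5 to 2.25 participants and q = 5% gives 7.5 to 11.25.

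**The case against.** The case for the plan is substantial. The rule is pre-specified and agrees across both documents, so it is a choice of reference and not a contradiction. The lead-in baseline precedes all atogepant in every arm. The SAP's summary of changes shows that some choices were made for an integrated safety summary, where a common reference is useful. The by-visit tables show the course from Week 4 to Week 40 against one reference, all assessments are listed, and nothing is tested. The Visit 1 limits in protocol 4.3 and 8.9, and the withdrawal for clinically significant laboratory abnormalities in 6.5.3, close much of the carry-over of high values. All of this stands. It narrows the point to lead-in placebo participants and to the exposed parameters above.

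Two stronger readings are tempting. First, because some participants stopped lead-in treatment and entered later ("When this extension study is initiated the participant should return to the clinic as soon as possible", with no upper limit on the gap), a reader might infer that every gap participant's change before Visit 1 is drug-free drift. The documents do not support this. Three of the four lead-in arms received atogepant, so for those participants the interval mixes time on and off drug. Rebaselining them at Visit 1 would subtract any lead-in drug effect still present.

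Second, a reader might quote the ratio within the placebo group, which is 1.4 (21.95/16.15) to 2.1 (4.07/1.96) in Illustration 1, as the inflation of the reported rate. The planned table is pooled, and the lead-in length, SD and random walk behind the ratio are all assumed.

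What the objection does not remove is that no planned table separates change on placebo from change on atogepant in this group, although the values to do so are collected.

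**Conclusion.** The point holds for lead-in placebo participants. Their change-from-baseline results, and the PCS counts that use change or are conditioned on baseline, combine the placebo period with the 40 weeks on atogepant. It matters mainly for weight, QTc and QTcF increase, and laboratory parameters with no numeric Visit 1 limit, and through lost denominators for laboratory, ECG and orthostatic PCS.

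The size cannot be derived from the documents, because lead-in length, allocation, drift and SD are not stated. On the assumptions of Illustration 1, the pooled end-visit rate of weight change of at least 7% rises by about 0.5 to 1.5 percentage points of 750. The planned table counts any postbaseline visit, so even this is only a rough guide. No stated number is wrong, and the adverse event tables are unaffected. This is a cheap improvement in attribution, not the correction of an error.

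**What to change.** Keep the lead-in baseline as the common reference for all participants, and as the only one for those who took atogepant in the lead-in.

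In SAP 11.0 and 18.3 add, for lead-in placebo participants, change-from-baseline and PCS tables for laboratory parameters, weight and vital signs, and ECG including QTcF. In these tables baseline is the last non-missing value before the first open-label dose. State that statements about change during the 40 weeks in this group will rest on them. Also state that this value is not a postbaseline value in these tables: the Week 4 window in SAP Table 18.1-1 starts at Day 1 and could otherwise take it in.

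The cost is SAP wording, a second baseline flag and a repeat of existing tables for a group that the SAP already identifies. No visit or procedure changes. The downside is two baselines to label clearly in the report.
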